Simulated Patient Encounters to Promote Early Detection and Engagement in Care for Adolescents (SPEED)

Grant Number: R01HD08507-01 Principal Investigator: [name], MPH, RN

Version Number: 7.0

May 11, 2020

LIST OF ABBREVIATIONS

APS	Adolescent package of services
ART	Antiretroviral therapy
CAB	Community advisory board
CCC	Comprehensive care clinic
CATCH	Counseling and testing for children at home
CEA	Cost-effectiveness analysis
CQI	Continuous quality improvement
DALY	Disability-adjusted life year
DASH	Developing adolescent strategies for HIV testing
FGD	Focus group discussion
FP	Family planning
GBV	Gender-based violence
HCW	Health care worker
HIV	Human Immunodeficiency Virus
IDI	In-depth interview
KNH	Kenyatta National Hospital
NASCOP	National AIDS and STI Control Programme
PMTCT	Prevention of mother-to-child transmission
PUSH	Pediatric urgent start of HAART
STI	Sexually transmitted infection
VCT	Voluntary counseling and testing
WHO	World Health Organization
SP	Standardized Patient Actor
YFS	Youth-friendly services

PROTOCOL SUMMARY

Title:	Simulated Patient Encounters to Promote Early Detection and Engagement in Care for Adolescents (SPEED)								
Objective:	This study aims to develop and evaluate a clinical training intervention utilizing standardized patient actors to improve communication and interpersonal skills of health care workers in working with adolescents, resulting in increased engagement in HIV care.								
Aims:	Aim 1: To develop case scripts specific to adolescent HIV care for use in SP encounters								
	Aim 2: To assess the impact of SP encounters on the likelihood of adolescent patients retained in care, and adherent to ART at public HIV treatment facilities in Kenya								
	Aim 3: To estimate the cost-effectiveness of SP training per adolescent retained in care								
Methods	Aim 1: Pilot testing and standardization of SP training tools and scoring with 10 health care workers (HCW) in HIV care								
	Aim 2: Stepped-wedge randomized controlled trial								
	Aim 3: Cost-effectiveness and cost-utility analysis								
Population:	Health care workers: Currently employed in HIV care services								
	Adolescents: HIV-infected boys and girls ages 10-24 years								
Number of Sites:	24 sites in Nairobi, Kiambu, Homa Bay, and Kisumu Counties in Kenya								
Study Duration:	4 years								
Outcomes	 Aim 1: Final scripts/ tools and scoring rubric for use in SP encounters Aim 2: Trial Primary Outcome: Retention in HIV care 								

1. BACKGROUND INFORMATION AND SCIENTIFIC RATIONALE

1a. Background Information

Sub-Saharan Africa has disproportionately high burden of adolescent HIV infection

Despite enormous expansion of HIV testing and treatment services in resource-limited settings, adolescents (ages 10-19) and youth (ages 20-24) continue to be substantially and disproportionately affected by HIV [1]. In 2012, an estimated 2.1 million adolescents were living with HIV, and 300,000 adolescents were newly infected [2]. And while mortality has decreased in adult and pediatric populations, there has been a 50% *increase* in adolescent HIV-related deaths over the last 7 years. Sub-Saharan Africa is home to 80% of adolescents and youth living with HIV globally [3]. Kenya alone accounts for 7% of all new adolescent HIV infections [2].

Substantial barriers for adolescent linkage to and retention in the HIV care cascade

Although HIV services have expanded throughout Africa, there has been less programmatic focus on adolescent HIV care than on adult care [1, 4, 5]. Inadequate provision of accessible and acceptable HIV testing, counseling, and treatment services is cited as a barrier to uptake of and retention in HIV care among adolescents [6]. For example, a recent Kenyan HIV treatment cohort study reported that 25% of youth and adolescents did not return after their first visit, 41% were lost in the first 12-months of the pre-ART period, and 21% of those initiating ART were lost within one year; rates higher than reported in adult programs [7]. Optimizing impact of HIV treatment programs requires early identification of HIV status, prompt linkage to care, and sustained adherence to antiretroviral therapy (ART). Loss throughout the care cascade translates to poor health outcomes and increased mortality, and subsequent HIV transmission due to uncontrolled viral load in all age groups. There is an urgent need for evidence-based interventions that promote adolescent uptake of and retention in HIV care [5].

HCWs lack confidence in their ability to provide HIV care for adolescents

A study of reproductive health HCWs in Kenya documented a disconnect between advertised "youth friendly services" and HCWs' lack of competency and training to carry out adolescent friendly care [8]. For example, while guidelines call for "adolescent friendly HIV testing", few details are provided to define what an "adolescent friendly" approach actually entails. Health HCWs expressed feeling a lack of competency in providing services to young people, especially related to counselling and interpersonal communication [8]. HCWs reported feeling conflicted between their own personal feelings, cultural and religious values and beliefs, and their wish to support young people's rights to accessing services.

In our preliminary studies, health care workers tasked with providing adolescent HIV testing services also reported feeling inadequately prepared to cope with the needs of this age group Themes included concern over adolescent depression and mental health, provider lack of confidence in counseling skills or fear of doing the wrong thing, concern over how to handle/advise adolescent disclosure and parental issues, and questions of adolescent autonomy and consent.

Adolescents have unique needs in HIV care and treatment

Few studies describe experiences of adolescents in accessing and engaging in HIV services. Adolescents experience unique physiological, developmental, and psychosocial changes that could potentially aggravate preexisting stressors associated with HIV infection [9-11]. Young people with HIV are particularly vulnerable to issues of mental health and depression, which can exacerbate poor adherence and retention in care [12]. Reported programmatic barriers include fear of harsh treatment by health care providers and lack of confidentiality or privacy in the health clinic [8].

Although adolescent-friendly policies exist, evidence-based interventions to improve health care workers competencies to provide high quality adolescent care are lacking

Globally, initiatives are underway to promote "adolescent friendly" health services. The WHO recommendations for adolescent friendly services include development of adolescent-specific skills and behaviors of health providers, assuring health facilities are appropriately equipped and appealing for adolescents, adolescents are aware of where they can obtain health services, and communities are aware and supportive of the health-services needs of adolescents. Adolescent friendly care aims to ensure that health providers are "non-judgmental and considerate in their dealings with adolescents" and that they have the "competencies to deliver the right health services in the right way" [13].

Patient-centered care is the missing link in the implementation 'know-do' gap to enhance adolescent HIV care

The impact and effectiveness of antiretroviral treatment (ART) is diminished by failure to adequately cover the adolescent population and to deliver services in an approachable and accessible manner. This type of "know-do" gap has been suggested to be rooted in lack of attention to *quality* in implementation of proven interventions like ART [14]. Quality of care is defined by the Institute of Medicine as safe, effective, **patient-centered**, efficient, timely and equitable [15]. Patient-centered communication, as defined by the Kalamazoo Consensus, includes building a relationship, opening discussion, gathering information, understanding the patient perspective, sharing information, reaching an agreement and providing closure [16]. These key components of care are often under-trained and under-implemented in resource-limited settings. A recent health facility assessment of HIV linkage and retention in care in Kenya noted that reported barriers (stigma associated with health facilities, poor provider-patient interactions) reflected a need for a new **patient-centered approach to HIV care** [17].

There is evidence that standardized patient actors improve quality of clinical care

Standardized patients (SPs) are trained actors that work with health care providers in mock clinical encounters for the purposes of training and evaluation [18]. Used since the 1960s in clinical and medical education and for licensing exams,[19] SPs are increasingly used as a mechanism to develop and improve skills related to patient-centered communication: empathy, communication skills, and counseling. As an evaluation tool, SPs are considered the gold-standard in measuring quality of care [19] and have been shown to accurately assess provider

performance in a variety of settings.[20-23] Not only are SPs an accurate measurement of care, reliably predicting provider behavior and clinical performance, but they can be used as a teaching mechanism. For example, in Mexico, training of delivery-room staff with low-tech simulations of obstetric emergencies resulted in improved process outcomes of health care provider knowledge and self-efficacy, but also significantly improved client health outcomes including perinatal mortality, eclampsia, and cesarean deliveries [24-26]. Other uses of actors include breaking bad news for oncology fellows [27], motivational interviewing training for community substance abuse providers [28], and end of life difficult conversations for surgical intensive care unit personnel.[29]

Improving clinical care and adolescent-friendly services may result in increased engagement in care

Despite clear guidelines for the type of behaviors and messaging to be practiced by health care providers, we are unaware of any scalable, evidence-based interventions that build adolescent friendly capacities in health care providers and that have been linked to improved adolescent care outcomes. A systematic review of adolescent friendly interventions found few rigorous studies of adolescent provider training programs [30]. Given the success of standardized patient and simulation programs in other settings, it is plausible that high-quality, patient-centered approaches could increase linkage to care, retention, and ART adherence among HIV-infected adolescents in sub-Saharan Africa.

1b. Rationale

An SP intervention for health providers has the potential to promote high-quality patient centered HIV services for adolescents by providing health workers with technical skills and pragmatic experiences. This improvement in delivery of care can, in turn, address barriers cited by adolescents and improve linkage to, and retention in, vital HIV services. By increasing engagement in care, the program can ultimately improve survival and decrease subsequent HIV transmission among adolescents in Kenya.

2. OBJECTIVES

2a. Study Objective

This study aims to develop and evaluate a clinical training intervention utilizing standardized patient actors to improve communication and interpersonal skills of health care workers in caring for HIV infected adolescents (ages 10-24 years), resulting in increased engagement in HIV care.

2b. Specific Aims

Aim 1: To develop patient case scripts specific to adolescent HIV-related care and counseling needs in Kenya, and to establish the number of training interactions necessary to reach competency

Hypothesis: Utilization of real-world adolescent experiences in a simulated patient actor training

program will improve health care provider communication and counseling skills with adolescents in Kenyan HIV care programs

Approach: Case scripts will be developed for male and female SP actors, derived from in-depth interviews with HIV-infected adolescents. We will establish competency scores and pass/fail cut-offs with a pilot sample of 10 health care workers (HCWs).

Aim 2: To assess the impact of SP encounters on the likelihood of adolescent patients retained in HIV care, and adherent to ART at public HIV treatment facilities in Kenya

Hypothesis: SP encounters will increase provider confidence and capacity to facilitate HIV status disclosure and provide supportive interactions with HIV-infected youth, which will significantly increase retention in HIV care and improve ART adherence among adolescents.

Approach: We will utilize a stepped wedge study design to assess retention in HIV services among HIV-infected adolescents. We will compare periods when clinics have received the SP training ('exposed periods') to 'control periods' prior to this training, when clinics are providing standard care. Data will be extracted via electronic medical records.

Aim 3: To estimate the cost-effectiveness of SP training per additional adolescent retained in care and cost-utility per life-year saved and per disability-adjusted life-year (DALY) averted for each adolescent

Hypothesis: An interactive SP training program will be cost-effective

Approach: We will measure detailed healthcare and program costs. We will use these costs to (1) estimate the short-term cost-effectiveness (measured as cost per additional adolescent retained in care) and (2), use modeling methods to estimate the long-term cost utility (measured as cost per disability-adjusted life-year averted).

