For the stepped-wedge randomized controlled trial, the 24 clinics will be randomized to *the time* when they receive the SPEED intervention. In this one-way cross-over design, all 24 sites will eventually receive the intervention. Groups of 6 clinics will be randomized to receive the intervention in one of four waves. We will use stratified randomization where facilities are also allocated to waves according to region and by facility size, defined as 'high volume', more than 73 AYA enrolled and medium volume, 73 or fewer AYA enrolled, based on the median, to ensure balance of characteristics in each wave [31]. A UW Biostatistician will generate the randomization assignment for each clinic in R Statistical Software (R Core Team, Vienna, Austria).

5g. Masking procedures

Because this a clinic training intervention using a pragmatic trial design, there will be no masking procedures.

5h. Participant Withdrawal

Participants may withdraw from the study at any time or the investigator may terminate a participant's participation.

Reasons for Withdrawal

Reasons for a study clinic to withdraw may include: clinic closure or major changes in HIV testing and treatment policies, procedures, or organization structural that would prevent or substantially limit our ability to conduct this study.

Reasons for HCW participant withdrawal may include: discomfort or distress as a result of the training, lack of time to complete the follow-up surveys, or job termination or relocation.

Reasons for an adolescent participant to not complete the satisfaction survey may include, lack of time, comfort, or interest in answering the questions.

An investigator may terminate a study participant's involvement in the study if **any medical condition or situation occurs such that continued participation in the study would not be in the best interest of the participant; or if** a HCW participant behaves in a way that disrupts or prevents the successful conduct of the SP encounter training.

Handling of participant withdrawals

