6. SPEED STUDY INTERVENTION

This study is evaluating a clinical training intervention utilizing standardized patients (SPs) that is anchored in social learning and behavioral theories [31, 32]. Standardized patients (SPs) are trained actors that work with health care providers in mock clinical training encounters, with a focus on improving communication skills and empathy. Through SP encounters, HCWs learn through cycles of concrete experiences, reflection, conceptualization, and active experimentation in a safe and controlled setting. We hypothesize that improved communication skills, competency, and empathy that HCWs will gain through this training will motivate adolescent patients to stay engaged in HIV care, including initiating and adhering to ART.

The clinical training intervention will consist of a combination of didactic sessions and SP encounters. Provider participants will receive orientation to the SP actor methodology as well as content related to communication skills and adolescent care. The intervention training schedule will be planned to minimize disruption to clinic operations.

For each wave of six clinics in the RCT, we estimate that it will take about 2 weeks (not more than 4 weeks) to train all HCWs in the Nairobi/Kiambu and Western Kenya sites. This timeframe will vary based on HCW availability and travel.

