8. STUDY SCHEDULE

In this trial, there will be 4 waves of 6 clinics per wave, and 5 measurement periods, including baseline (Table 3). Total duration of the trial is approximately 3 years. Each wave will be rolled out approximately every nine months. Data pulls will occur 15 months after the HCW training, to ensure that all clients who present within the exposure time period have a full 6 months to return for care.

	Introduction of Intervention									
Clinic clusters	Baseline	Month 1	Month 10	Month 19	Month 28					
Wave 1: Sites 1-6	0	Х	Х	Х	Х					
Wave 2: Sites 7-12	0	0	Х	Х	Х					
Wave 3: Sites 13-18	0	0	0	Х	Х					
Wave 4: Sites 19-24	0	0	0	0	Х					

An overview of the anticipated overall study schedule for one wave is shown in Table 4, following page. The study will be conducted over five years. During year one, we anticipate script development, recruiting and training SPs, developing measurement checklists, and piloting initial encounters at Kenyatta National Hospital. During year two, we will recruit and randomize study sites, and begin implementation of the intervention. The intervention will be rolled out in waves, completing measurement and intervention cycles during year 4. Year 5 will be dedicated to statistical outcome analyses, cost effectiveness analyses and modeling, and dissemination of study findings both locally and internationally.

SPEED Protocol Protocol # Version 7.0 May 11 2020

Table 4. Overview of SPEED Study 2015 - 2020

	Y1		Y2			Y3			Y4				Y5							
	Q1	Q2	Q3	Q4																
Study Planning		1		I	1		I													
Protocol development																				
IRB Submissions																				
Implementation	r			1	1	ī	r	Ū	ī											
Site selection																				
Actor Training																				
Pilot phase																				
Consents & Randomization																				
Baseline OR EMR data pull					х				х				х				х	х		
Wave 1																				
Training																				
Exposure time & data pull (X)									Х											
Wave 2					Х															
Training																				
Exposure time & data pull (X)												Х								
Wave 3					Х															
Training																				
Exposure time & data pull (X)															Х					
Wave 4					Х															
Training																				
Exposure time & data pull (X)																		Х		
Post-trial data pull																			Х	
Analysis																				
Data Analysis																				
Dissemination	1	1		1			1													

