12. STATISTICAL CONSIDERATIONS

12a. Sample Size Considerations

For the Aim 2 RCT, we based our sample size and power calculations on the primary outcome of retention in care, obtained from EMR data. This outcome is binary on the individual level. We used the methods described by Hussey and Hughes [32] to determine power assuming an evaluation with 24 clusters and 5 time points (including baseline). We include 24 clinics in this study to account for the possibility that 15% drop-out without replacement. We assumed that only a small proportion of the 40 HIV-positive adolescents enrolled in HIV care per clinic may be newly enrolled or recently re-engaged in care. As such, we estimated the minimum number of records per clinic for 80% power to detect a 15% difference between control and intervention periods. We assumed a coefficient of variation (τ/μ) of 0.25 and calculated the power for a two-tailed test with α =0.05. Based on relevant published data [7], we assumed that 75% of adolescents in the control period will return to clinic after first visit. Under these assumptions, we estimate needing at least 5 adolescents per clinic. As such, the lower bound of the sample size required is estimated to be 720 clinic records (6 records/site X 24 sites X 5time points). If N=20

clinics are retained, we would need 7 adolescents per site, per time point, or a minimum of 700 records total.

In the optimal scenario with an average of 40 adolescents in care at each facility, our estimated analysis sample size would be at least 4,800 (5 time points). Under the same assumptions described above, we would have >99% power to detect a 15% difference in retention between the intervention and control periods.

We expect to have adequate power to detect an intervention effect for the analysis with a broader definition of retention in care (return for any follow-up visit within 6 months), because this is likely a more common pattern of follow-up than either return among newly enrolled or return after re-engagement in care.

12b. Planned interim analyses (if applicable)

Because this is a randomized trial with a stepped-wedge (staggered roll-out) design, there will be no interim analyses or stopping rules.

12c. Overview of analysis plan

Pilot phase

Qualitative feedback from participants, actors, and faculty experts will be used to finalize the case scripts, actor checklist, and HCW satisfaction survey.

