Data from the completed faculty checklists will be used to establish competency scores. Participants, faculty experts, and actors will be asked to provide qualitative feedback on the checklist indicators. Inter-rater reliability of the faculty checklist will be determined using Cohen's kappa. We will assess correlation of checklist variables and utilize principal component analysis to reduce the number of variables, using a scree test method to plot eigenvalues. Pass/fail cutoff scores will utilize relative and absolute standard-setting processes [33]. In relative processes, initial pass/fail determinations will depend on the performance of the cohort, such that all scoring less than 1 standard deviation below the mean receives a fail. Relative standards are useful with new trainings where there is no prior performance data. Subsequently we will explore standard-setting using an iterative combination of the Angoff item-based method and the Hofstee whole-test method. The Angoff method establishes the probability of a borderline student to accomplish each item on the checklist. The sum of probabilities across items is then equal to a passing score. A team review process is convened in which reviewers discuss outlier ratings, assess performance data after pilot testing, and revision of ratings if necessary. The Hofstee whole-test method combines normative and absolute judgments, in that checklist reviewers make four determinations: the minimum and maximum acceptable passing scores. and the minimum and maximum proportions of students failing. A final cut-off determination will be made by averaging the Hofstee and Angoff scores.

Stepped-Wedge Randomized Controlled Trial

The primary analysis will be an intent-to-treat (ITT) analysis, assuming that adolescents who receive care at clinics after the SPEED training will be 'exposed' to HCWs trained in the SPEED intervention until the end of the study.

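### The primary analysis is labelled intent-to-treat, but exposure is worded by receipt of training, and no rule covers a clinic that is trained late, never trained or withdrawn

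*Combined protocol and SAP*

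**What the plan says.** Section 5f fixes the unit and content of randomisation: "Groups of 6 clinics will be randomized to receive the intervention in one of four waves". Table 3 in section 8 shows the planned switch from control to intervention for each wave.

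The comparison is then worded by a different event. Section 2b, under Aim 2, reads: "We will compare periods when clinics have received the SP training ('exposed periods') to 'control periods' prior to this training". Section 12c reads: "The primary analysis will be an intent-to-treat (ITT) analysis, assuming that adolescents who receive care at clinics after the SPEED training will be 'exposed", and goes on to say that this exposure is to trained staff and lasts to the end of the study. Section 8 also anchors follow-up on the training: "Data pulls will occur 15 months after the HCW training".

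In the model of section 12c the exposure term Xij is indexed by clinic and time and described only as the intervention. It is not defined by the randomised wave or by the training date.

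On departures from schedule, section 6 expects each wave to take "about 2 weeks (not more than 4 weeks) to train all HCWs" and adds: "This timeframe will vary based on HCW availability and travel". Section 5h allows a clinic to withdraw, for example on closure or major reorganisation. Section 12a says: "We include 24 clinics in this study to account for the possibility that 15% drop-out without replacement". No section says how the primary analysis treats a clinic that missed its slot, was never trained or withdrew.

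**The concern.** In a stepped-wedge trial, the protection against confounding at clinic level comes from the randomised timing of the switch. An intent-to-treat analysis keeps it by coding each clinic according to its assigned wave. Coding by the date on which training happened keeps it only while the two dates agree.

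Once a clinic misses its step, receipt-based coding moves that clinic-period from the exposed to the control side, for a reason that was not randomised. If that reason also affects whether adolescents return, the primary estimate is biased. Dropping a withdrawn clinic likewise removes a randomised unit for a reason arising after randomisation. The primary retention result, and the cost per additional adolescent retained that is built on it, would carry the error under an intent-to-treat label.

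**Working it through.** **1. The plan's own power figure.** Inputs from section 12a: 24 clinics, 5 time points, control return 0.75, a 15-point difference (so 0.90), coefficient of variation 0.25, two-sided 5%. Then τ = 0.25 × 0.75 = 0.1875 and τ² = 0.035156. The binomial variance at the mean rate is 0.825 × 0.175 = 0.144375.

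Hussey and Hughes, with s = 0.144375/n:

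Var = I·s·(s + T·τ²) / [(I·U − W)·s + (U² + I·T·U − T·W − I·V)·τ²]

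- U = 6 × (4+3+2+1) = 60
- W = 6² + 12² + 18² + 24² = 1,080
- V = 6 × (16+9+4+1) = 180
- I·U − W = 1,440 − 1,080 = 360
- U² + I·T·U − T·W − I·V = 3,600 + 7,200 − 5,400 − 4,320 = 1,080

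At n = 5, s = 0.028875. Numerator: 24 × 0.028875 × (0.028875 + 0.175781) = 0.14183. Denominator: 360 × 0.028875 + 1,080 × 0.035156 = 48.364. Var = 0.002933, SE = 0.0542, and power = Φ(0.15/0.0542 − 1.96) = 79.1%. Averaging the two binomial variances instead gives 80.6%. The plan's 80% at 5 per clinic therefore reproduces, and 40 per clinic gives more than 99.9%. This calculation assumes that every clinic crosses over on its randomised schedule, so it does not test the present point.

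**2. How close the two codings are on schedule.** Section 8 says: "Each wave will be rolled out approximately every nine months". Nine months is about 39 weeks, so the 4-week upper limit on training is 4/39, about 10% of a step. On time, the choice of coding hardly matters.

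**3. One-step delay, no true effect.** The documents give no delay rate, so these settings are assumptions. In each clinic-period a temporary disruption occurs with probability 1/12 or 1/8. It lowers return by 10 or 20 points. If it falls in the training slot, it delays training by one step. Expected late clinics: 24/12 = 2 and 24/8 = 3. The model is linear, with fixed periods and a random clinic effect, with τ and variance as in step 1 and 4,000 simulated trials per setting. Mean estimate under receipt coding (the truth is 0):

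| Late clinics | Drop | 6 records per clinic-period | 40 records |
|---|---|---|---|
| 2 | 10 points | +0.0145 | +0.0160 |
| 2 | 20 points | +0.0287 | +0.0306 |
| 3 | 10 points | +0.0201 | +0.0222 |
| 3 | 20 points | +0.0439 | +0.0433 |

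Randomised-wave coding of the same data stays within 0.0012 of zero.

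**4. Varying the link between delay and retention.** A second simulation used 40 records per clinic-period, a between-clinic SD of 0.0625 (to keep probabilities below 1) and a cluster-robust SE with critical value 2.07. A disruption probability of 10% or 20% delays about 24 × 0.10 = 2.4 or 24 × 0.20 = 4.8 clinics, and training is postponed for as long as the disruption lasts.

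| Shift in retention when delayed | 2.4 clinics: bias (false positives) | 4.8 clinics: bias (false positives) |
|---|---|---|
| −15 points | +0.026 (18%) | +0.049 (43%) |
| −10 points | +0.018 (12%) | +0.033 (26%) |
| none | 0.000 (7%) | 0.000 (6%) |
| +10 points | −0.018 (13%) | −0.033 (31%) |

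Randomised-wave coding gave mean estimates between −0.0014 and +0.0005 and false-positive rates of 4.5% to 6.2%. If instead the clinics are never trained, are persistently 10 points worse and are coded control, the bias is only +0.009 to +0.016, because the clinic random effect absorbs part of the difference.

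The near-zero result for wave coding rests on disruptions falling independently of the assigned wave. A drop caused by the assigned slot itself would enter the wave-coded estimate too, as part of the effect of assignment.

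**The case against.** The strongest reply is that the plan states no wrong rule. Section 2b is a summary of aims. The section 12c sentence can be read at patient level: everyone attending after roll-out counts as exposed, whichever member of staff they see. Table 3 lays out exposure by wave, and section 12c reports each clinic's assignment per period. All of this is compatible with coding by schedule. It stands as a reason to call this an ambiguity. It does not settle the matter: Table 3 is the planned roll-out, the assignment wording describes the CONSORT diagram, and neither defines Xij.

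Three stronger readings are tempting, and the documents do not support them.

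- A reader might infer that a withdrawn clinic would be coded control throughout. No text says so. Section 12a recalculates for 20 retained clinics and section 12c reports excluded clusters, which points to dropping. Section 5d allows exclusion of a facility that cannot be trained, without saying whether this applies after randomisation.
- A reader might infer that the plan expects clinics to miss whole steps. The remark in section 6 about variation concerns how long a wave's training takes, and it follows a 4-week limit.
- A reader might infer that the bias favours the training. That direction was built into the settings of step 3. The second table shows no bias or false harm under other assumptions.

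The simulations also use a linear model, where the plan has a Poisson mixed model with robust standard errors. The first set takes its variance at the mean of 75% and 90% although no effect is simulated. The sizes are therefore illustrative.

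**Conclusion.** The point holds as a gap between label and definition. The primary analysis is called intent-to-treat, exposure is worded by receipt of training, and late, untrained and withdrawn clinics have no stated handling. Followed literally, the wording gives as-treated coding for any clinic that misses its step. Dropping withdrawn clinics would not be intent-to-treat either.

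The consequence is small or nil if training keeps to schedule. With 2 to 3 clinics one step late and a coinciding 10 to 20 point fall in return, the false benefit is about 1.5 to 4.4 points, or 10% to 29% of the 15-point design difference (1.5/15 and 4.4/15). It is zero without a link between delay and retention, and negative if delayed clinics retain better. The delay rates and shifts are assumptions. The case for acting does not depend on them, because wave-based coding gives practically the same answer when all goes to plan.

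**What to change.** In sections 2b and 12c, define Xij = 1 from the start of the period of the wave to which clinic i was randomised, whatever the actual training date and whether or not training took place. State that late, untrained and withdrawn clinics stay in the primary analysis by assignment wherever EMR records exist. Say whether the facility exclusion in section 5d can apply after randomisation. Report coding by actual training as a sensitivity analysis, with the number of clinics that departed from schedule and the reasons.

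The cost is a few sentences and one recoded variable, settled before the outcome analysis. The data-pull timing in section 8, now counted from training, needs to be aligned with the wave period. A closed clinic may have no further records, so the rule can reach only as far as the EMR does. The statistical downside is some dilution of the estimated effect if clinics are late, which is what an intent-to-treat estimate should show.
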